			
Germany): Questions 15.1.a – 15.3.
 
Questions about Prescriber Treatment Checklist for tofacitinib (Germany only): Questions 14.1.i.a. - 14.4.i.
 
Questions about tofacitinib patient alert cards (All Countries): Questions 16.1a – 16.2.
 
Questions about the prescriber website for tofacitinib (All Countries): Questions 17.1 – 17.3.
 
*In addition to asking about the HCP’s ever receipt of the aRMM materials, questions were added about the receipt of each materials after February 2020 (or after January 2020 for Poland) (Questions: 13.1b, 14.1b., 15.1b, 14.1.i.b, 16.1b).
 
The response options pertaining to usefulness (current questions: 13.3, 14.3, 15.3, 14.4.i, 16.2, 17.3) were simplified from: “Not useful”, “Somewhat useful”, “No opinion/not sure”, “Very useful”, “Extremely useful”, Did not receive material/did not visit Xeljanz Prescriber Website”
	
To distinguish between the HCP’s ever receiving the aRMM materials vs. the receipt of the most recently updated version post Article 20 procedure, questions were added about the receipt of each material after February 2020.
 
The response options to the usefulness questions were changed to simplify and allow better discernment between options. During HCP user testing it became clear that the “no opinion” option was not interpreted consistently; this could have led to measurement error.

090177e199ebc283\Approved\Approved On: 11-Apr-2022 22:32 (GMT)

Amendment number	Date	Protocol section(s) changed	Summary of amendment(s)	Reason
			To: "Very useful", "Somewhat useful", "Not useful"	
			Changes made to the Rheumatoid Arthritis and Psoriatic Arthritis survey were also made to the Ulcerative Colitis (UC) survey. Those changes are not described again.	The two surveys are nearly identical.
2 (Version 3.0)	28 March 2022	3. Abstract 5. Milestones 8.1 Study Design	The dates for the registration in the EU PASS register, SAP finalization, start of data collection, end of data collection and final study report submission were changed to the following dates: Registration in the EU PASS register: 29 September 2021 Statistical Analysis Plan (SAP) finalization: 28 February 2022 Start of Data Collection: 01 November 2021 End of Data Collection: 18 April 2022 Final Study Report Submission: 18 April 2023	Updating to match RMP, justification for milestone changes communicated to EMA in a regulatory response as part of Procedure EMEA/H/C/004214/IB/0042/G

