8.2. Setting

Eight countries were selected for the survey: France, Germany, the Netherlands, Poland, Romania, Spain, Sweden, and the UK. Country selection was based on a combination of factors that make them the most operationally feasible European countries in which to implement the survey and most likely to yield a meaningfully large and representative sample of HCPs treating patients for RA, PsA, or UC. Those factors included:

- Highest numbers of potential Xeljanz prescribers (e.g., rheumatologists, dermatologists, and gastroenterologists);
- Highest projected number of patients to be treated with Xeljanz (data not shown as they are based on projections that are subject to change);
- Timing of Xeljanz reimbursement and aRMM materials distribution; and
- Geographic location (the selected countries represent Western, Northern, Southern, and Eastern Europe).

Table 1 shows the timetable for projected Xeljanz availability with full reimbursement, projected current aRMM materials distribution, and estimated windows for survey data collection.

Table 1. Provisional Dates for Xeljanz Availability with Full Reimbursement, aRMM Materials Distribution, and Estimated Start and End of Survey Data Collection in Selected European Countries

Country	Indication	Date Product fully Available on Market (i.e., with reimbursement)	Date Current aRMM Materials Available to All Potential HCPs	Window for Data Collection (i.e., start and end dates for data collection) ^a
Germany	RA	May 2017	20 March 2020	23 November 2021 – 01 March 2022
	PsA	June 2018		
	UC	July 2018		
UK	RA	January 2018	6 March 2020	01 November 2021 – 07 February 2022
	PsA	October 2018		
	UC	August 2018		
Netherlands	RA	May 2017	11 May 2020	01 November 2021 – 07 February 2022
	PsA	August 2018		
	UC	September 2018		
Sweden	RA	April 2017	5 March 2020	01 November 2021 – 07 February 2022
	PsA	October 2018		
	UC	October 2018		
Spain	RA	October 2017	30 November 2020	01 November 2021 – 07 February 2022
	PsA	August 2019		
	UC	August 2019		
France	RA	December 2017	29 April 2020	08 November 2021 – 15 February 2022
	PsA	July 2019		
	UC	July 2019		
Poland	RA	September 2019	05 February 2020	01 November 2021 – 07 February 2022
	PsA	Expected March 2020		
	UC	Expected March 2020		
Romania	RA	December 2019	26 August 2020	17 January 2022 – 25 April 2022 (tentative)
	PsA	Expected September 2020		
	UC	Expected September 2020		

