8.3. Variables

The variables to be analysed will include:

1. HCP practice characteristics.

- Specialty (i.e., In the RA/PsA Survey: rheumatology, dermatology or other and in the UC survey: gastroenterology, or other);
- Number of years in practice;
- Experience prescribing Xeljanz within the past 12 months for RA and/or PsA or UC;
 - This variable will be used as a proxy for indication. An HCP who has experience prescribing Xeljanz for multiple indications (of RA and PsA) will be classified in the indication that corresponds to the HCP’s highest specialty designation in the OneKey database;
- Self-reported most recent prescription for Xeljanz for RA and/or PsA or UC;
- Self-reported approximate number of Xeljanz prescriptions written for RA and/or PsA or UC in the past 12 months;

⁴ HCPs who respond to the survey but are not rheumatologists, dermatologists, or gastroenterologists (e.g., nurse practitioners, physician’s assistants, physicians of other specialties) will be allowed to participate if they are prescribers of Xeljanz for patients diagnosed with RA and/or PsA or UC and meet the study inclusion/exclusion criteria.

- Self-reported approximate number of patients prescribed Xeljanz for RA and/or PsA or UC in the past 12 months;
- Role in providing Xeljanz treatment (i.e., only initiation, both initiation and maintenance, only maintenance); and
- Prior participation in a Pfizer-sponsored tofacitinib clinical trial as a healthcare professional.

Note: There are 2 questions that ascertain information on the HCP's specialty and years of practice and 7 questions in the RA/PsA survey and 6 questions in the UC survey that ascertain information on the HCP's experience prescribing Xeljanz (see survey instrument in Appendix 1 and Appendix 2 [HCP Questionnaire for RA/PsA and UC, respectively]).

2. aRMM program implementation.

- Awareness (receipt) of each of the aRMM materials *ever* (i.e., whether the respondents recalled receiving each of the following aRMM materials: the Xeljanz Prescriber Brochure, the Xeljanz prescriber treatment checklists, and the Xeljanz Patient Alert Card);
- Awareness (receipt) of each of the aRMM materials *after February 2020 (or after January 2020 for Poland)*;
- Utilisation of each of the aRMM materials (i.e., whether the respondents read the Xeljanz Prescriber Brochure, utilised the Xeljanz prescriber treatment checklists when prescribing Xeljanz), and distributed the Xeljanz Patient Alert Card to their patients); and

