
 Awareness (Receipt) after February 2020 	
≥80% of HCPs reporting that they received 4 out of the 4 (100%) aRMM materials⁵ in all countries, except for Germany
 
≥80% of HCPs reporting that they received 3 out of the 3 (100%) aRMM materials⁶ in Germany
	
≥80% of HCPs reporting that they received 4 out of the 4 (100%) aRMM materials⁵ in all countries, except for Germany
 
≥80% of HCPs reporting that they received 3 out of the 3 (100%) aRMM materials⁶ in Germany

 Knowledge 	
≥80% of HCPs correctly answering ≥14 out of 18 (≥78% [or approximately 80%]) of the knowledge questions
	
≥80% of HCPs correctly answering ≥16 out of 20 (≥80%) of the knowledge questions

 Adherence 	
≥80% of HCPs providing desirable responses for ≥14 out of 17 (≥82% [or approximately 80%]) of the adherence questions
	
≥80% of HCPs providing desirable responses for ≥14 out of 17 (≥82% [or approximately 80%]) of the adherence questions

Note: The measures of effectiveness in each of the 4 domains listed above will be calculated variables.

⁵ The 4 aRMM materials include: the Xeljanz Prescriber Brochure, the Xeljanz Prescriber Treatment Initiation Checklist, the Xeljanz Prescriber Treatment Maintenance Checklist, and the Xeljanz Patient Alert Card. As the Xeljanz Prescriber Website is a repository for the aRMM materials, rather than a tool in and of itself, awareness of the Xeljanz Prescriber Website will not be considered when evaluating the effectiveness of the entire aRMM program.

⁶ The 3 aRMM materials include: the Xeljanz Prescriber Brochure, the Xeljanz Prescriber Treatment Initiation and Maintenance Checklist, and the Xeljanz Patient Alert Card. As the Xeljanz Prescriber Website is a repository for the aRMM materials, rather than a tool in and of itself, awareness of the Xeljanz Prescriber Website will not be considered when evaluating the effectiveness of the entire aRMM program.

6. Attitude toward the aRMM materials (i.e., how useful the HCPs find the various aRMM materials in their practice).

- There are 5 survey questions (1 question for each of the aRMM materials plus 1 question for the Xeljanz Prescriber Website) that ascertain HCPs' attitudes towards the aRMM materials, except for Germany, which has 4 questions.

7. Source of HCPs' information on the safety of Xeljanz.

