a	Educational materials (documents designed for the patient and the physician, such as the tofacitinib prescriber brochure, the prescriber initiation and maintenance checklists, and the patient alert card)	
b	Summary of Product Characteristics (Label)	
c	National Health Authority website/National formulary website	
d	Pharmaceutical company website	
e	Do not know/recall the source	
f	Other	

Data: Single punch.

Data: Answer options will be displayed in a random order for each survey participant, with an exception for "Do not know" and "Other" – always keep these as the last two options.

[QUESTIONS ABOUT AWARENESS (RECEIPT) AND UTILISATION OF TOFACITINIB aRMM MATERIALS]

[QUESTION APPLIES TO ALL COUNTRIES]

Q13.1a. Have you ever received a **prescriber brochure for tofacitinib**? Please select one.

- Yes
- No
- I don't remember

Data: Single punch.

[QUESTION APPLIES TO ALL COUNTRIES, EXCEPT POLAND]

Q13.1b. The **prescriber brochure for tofacitinib** was updated in 2020. Did you receive a prescriber brochure after February 2020? Please select one.

- Yes
- No
- I don't remember

Data: Single punch.
Ask only if Yes in Q13.1a.

[QUESTION APPLIES TO POLAND ONLY]

Q13.1b. The **prescriber brochure for tofacitinib** was updated in 2020. Did you receive a prescriber brochure after January 2020? Please select one.

- Yes
- No
- I don't remember

Data: Single punch.
Ask only if Yes in Q13.1a.

[QUESTION APPLIES TO ALL COUNTRIES]

Q13.2. Have you read the **prescriber brochure for tofacitinib**? Please select one.

- Yes, all of it
- Yes, some of it
- No, I did not read it
- I don't remember

Data: Single punch.

Ask only if Yes in Q13.1a.

[QUESTION APPLIES TO ALL COUNTRIES]

Q13.3. How useful or not useful do you find the **prescriber brochure for tofacitinib** in your clinical practice?

- Very useful
- Somewhat useful
- Not useful

Data: Single punch.

Ask only if Yes in Q13.1a.

[QUESTION APPLIES TO ALL COUNTRIES EXCEPT GERMANY]

Q14.1a. Have you ever received the **prescriber treatment initiation checklist for tofacitinib**? Please select one.

- Yes
- No
- I don't remember

Data: Single punch.

[QUESTION APPLIES TO ALL COUNTRIES EXCEPT GERMANY and POLAND]

Q14.1b. Did you receive the **prescriber treatment initiation checklist for tofacitinib** after February 2020? Please select one.

- Yes
- No
- I don't remember

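### The 'after February 2020' receipt criterion predates full availability of the updated materials by up to 59 to 274 days in four of the eight countries, so it cannot be read there as receipt of the current version

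*Protocol*

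**What the plan says.** Protocol Section 8.3 (Variables), item 2, defines receipt of each material ever and, separately, "after February 2020 (or after January 2020 for Poland"). Item 5 makes "Awareness (Receipt) after February 2020" an effectiveness criterion in its own right. Success is "≥80% of HCPs reporting that they received 4 out of the 4 (100%) aRMM" materials, or 3 of 3 in Germany. The row carries only the February label.

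The wording put to respondents is in Appendix 1, Q13.1b: "Did you receive a prescriber brochure after February 2020". The Polish version reads "Did you receive a prescriber brochure after January 2020". The checklist and alert-card questions (Q14.1b, Q15.1b, Q14.1.i.b, Q16.1b) use the same cut-offs, as does Appendix 2.

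The purpose is given in the reason column of the amendment log (Section 4): to separate ever-receipt from "the receipt of the most recently updated version post Article 20 procedure". Section 6 calls this version the current aRMM materials and refers to Table 1 for each country's date. Table 1 in Section 8.2 lists when the current materials were available to all potential HCPs. The latest dates are "30 November 2020" (Spain) and "26 August 2020" (Romania).

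**The concern.** A date can stand in for a version only if the new version had replaced the old one by that date. In four countries Table 1 places full availability about two to nine months after the cut-off. Earlier versions had been in distribution since April 2017 (Section 6), so an HCP could have been sent a superseded copy in that interval. The answer would be truthful and would still be scored as a success.

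The updated version carries the Article 20 findings on VTE, mortality and patients over 65, and the study is meant to show whether the materials were implemented as intended. A met criterion could be reported as delivery of the update when it shows only delivery of some version. Section 8.9.1 also offers a comparison of recipients with non-recipients in place of the missing baseline. If that comparison used this variable, the recipient group could include HCPs who hold only the old text.

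**Working it through.** **Inputs.** Cut-offs: Section 8.3 and Appendix 1. Availability dates: Table 1. Specialist counts: Appendix 5. Precision: Section 8.5.

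**The plan's own size figure.** The half-width at n = 300 and P = 50% is 1.96 × √(0.25/300) = 5.66%, which matches the stated 5.7%.

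**Gap between cut-off and full availability.** Days = Table 1 date minus the first day after the cut-off month (1 March 2020; 1 February 2020 for Poland).

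| Country | Table 1 date (2020) | Gap (days) |
|---|---|---|
| Spain | 30 November | 274 (9.0 months) |
| Romania | 26 August | 178 (5.8 months) |
| Netherlands | 11 May | 71 (2.3 months) |
| France | 29 April | 59 (1.9 months) |
| Germany | 20 March | 19 |
| UK | 6 March | 5 |
| Sweden | 5 March | 4 |
| Poland | 5 February | 4 |

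The gaps fall into two groups: 4 to 19 days in four countries and 59 to 274 days in the other four. Poland's cut-off is the month before its Table 1 date, so a country-specific date was feasible.

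**Share of the sampling frame in the affected countries.**
- RA/PsA (rheumatology plus dermatology): Spain 4,166 + Romania 1,394 = 5,560 of 30,231 = 18%. Adding France 6,941 and the Netherlands 1,158 gives 13,659 of 30,231 = 45%.
- UC (gastroenterology): 3,842 + 566 = 4,408 of 17,452 = 25%. Adding 4,367 and 762 gives 9,537 of 17,452 = 55%.

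**Illustration only.** The documents give no rate of false successes. Assume that 5% to 20% of respondents in the affected countries meet the criterion only because of superseded copies, and that respondents are spread as in Appendix 5. The pooled, unweighted proportion then rises by (frame share) × (assumed rate):
- Spain and Romania only: 0.9 to 3.7 points (RA/PsA), 1.3 to 5.1 points (UC).
- All four countries: 2.3 to 9.0 points (RA/PsA), 2.7 to 10.9 points (UC).

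The lower ends are well inside the 5.7% precision and the four-country upper ends exceed it. One rate for all four countries is generous, because the French window is about a fifth of the Spanish one (59/274).

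**The case against.** The strongest reply is that the window is not the misclassification. An old copy received in the gap gives a wrong success only if the HCP did not receive the update later. Fieldwork opened about 11 months after Spain's date and nearly 17 months after Romania's. The HCP must also report every material after the cut-off. Nothing in the protocol says that superseded copies were still going out. Table 1, which is headed as provisional, dates availability to all potential HCPs, so some may have had the update sooner. All of this stands: the day counts are upper bounds on the window and say nothing about how many HCPs are affected.

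A reader might infer that the error can only inflate the criterion. The documents do not support that. The European Commission approved the revisions on 31 January 2020 (Section 6), so an HCP who received the update in February 2020 would truthfully answer 'No'. Section 8.9.2 also allows recall error in either direction.

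A reader might also take the frame shares as the size of the bias. They are counts by primary specialty, only some of whom prescribe. Dermatologists make up 21,099 of the 30,231, and Section 8.5 doubts how many of them manage eligible patients. In Romania, PsA and UC reimbursement was expected in September 2020, after that country's Table 1 date, so prescribers for those indications are weaker candidates for an old copy.

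It can be said further that the operative text names a date and not a version, that Q13.1b tells respondents the brochure was updated in 2020, and that the knowledge and adherence items test VTE and age-65 content directly. The first point supports labelling the result by date. The cue is absent from the checklist and alert-card questions. The content items measure knowledge and self-reported practice, and cannot show which version was delivered. The recall limitation in Section 8.9.2 does not cover this problem, which arises even with perfect recall.

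**Conclusion.** The point holds in a limited form. In France, the Netherlands, Romania and Spain the criterion measures receipt after a date that precedes full availability of the current materials by up to 59, 71, 178 and 274 days. A truthful 'Yes' for a superseded copy alone counts towards the 80% threshold. In Germany, the UK, Sweden and Poland the gap is 4 to 19 days and the date is a reasonable proxy for the version.

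The net effect is probably upward, because in these four countries the gap leaves long room for false successes, while missed early recipients need delivery before March 2020. Its size cannot be determined from the protocol. The conclusion assumes that the Table 1 dates are right and that some superseded copies were still reaching HCPs in the gap. It does not show that the criterion will be met wrongly, only that meeting it would not establish delivery of the update in these four countries.

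**What to change.** By version 3.0 (28 March 2022) every Table 1 data collection window except Romania's (tentatively to 25 April 2022) had closed. Rewording Romania's questions in mid-field would mix two versions of the question. The remedy therefore lies in definition and reporting:

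1. Define and label the criterion in Section 8.3, item 5, as receipt after a stated date, with the Polish date shown, and not as receipt of the current version.
2. Report it by country. Section 8.7.1 leaves country strata optional; for this criterion they should be fixed.
3. Repeat the pooled figure without Spain and Romania, then also without France and the Netherlands.
4. Draw any conclusion that the current version was received only from Germany, the UK, Sweden and Poland.
5. In any future questionnaire, set each country's cut-off from its own Table 1 date, as 'since' that month or 'after' the preceding month as in Poland, or identify the version. Asking about receipt 'after' the Table 1 month itself would reject true recipients, for example in the Netherlands, where the date is 11 May.

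No new data are needed. The cost is that fewer countries support the current-version claim, with less precision. If 300 completed surveys were spread as in Appendix 5, the four remaining countries would supply about 164 for RA/PsA (300 × 16,572/30,231) and 136 for UC (300 × 7,915/17,452). The half-widths at P = 50% would be 1.96 × √(0.25/164) = 7.7% and 1.96 × √(0.25/136) = 8.4%, against 5.7%.

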Appendix 2. HCP Questionnaire for Ulcerative Colitis

[SCREENING QUESTION]

[QUESTION APPLIES TO ALL COUNTRIES]

Before starting the survey, we need to ensure that you are eligible for this survey by asking you the following question:

S1. Are you currently employed by Pfizer?

No *Continue*

Yes Thank you for your interest. Unfortunately, you are not eligible to participate.
Close (SCREEN OUT).

(yes/no tick box)

If you have any questions, please contact: IQVIA Team at: *xxxxx [to be adapted to the country]*.

Kind regards,

IQVIA Team

Start of Interview:

[QUESTIONS ABOUT HCP PRACTICE CHARACTERISTICS]

[QUESTION APPLIES TO ALL COUNTRIES]

Thank you for your interest in this study. This survey should take about 25 minutes to complete and consists of 5 sections. It should be completed in one sitting.

The first section includes questions about your professional background and practice.

D1. What is your main medical specialty? Please select one.

a	Gastroenterologist	
b	Other	

Data: Single punch.

[QUESTION APPLIES TO ALL COUNTRIES]

D2. After completing all specialist training, for how many years have you been in practice? Please select one.

a	Less than 1 year	
b	1 year to less than 5 years	
c	5 years to 10 years	
d	More than 10 years	

Data: Single punch.

[QUESTIONS ABOUT EXPERIENCE WITH XELJANZ (TOFACITINIB)]

Thank you. The second section of questions asks about your experiences with Xeljanz (tofacitinib).

[QUESTION APPLIES TO ALL COUNTRIES]

S2. Within the past 12 months, have you prescribed tofacitinib for ulcerative colitis? Please consider both new and repeat prescriptions.

a	No		Thank you for your interest. Unfortunately, you are not eligible to participate. Close (SCREEN OUT)
b	Yes		Continue

(yes/no tick box)

[QUESTION APPLIES TO ALL COUNTRIES]

Q1. When was the last time you prescribed tofacitinib? Please consider both new and repeat prescriptions. Please select one response.

a	Within the past 6 months	
b	More than 6 months ago	

Data: Single punch.

[QUESTION APPLIES TO ALL COUNTRIES]

Q2. Within the last 12 months, how many **prescriptions** for tofacitinib have you written for ulcerative colitis? Please think of **the total number of prescriptions** – both new and repeat – and not the number of patients. Please select one.

a	Fewer than 10 prescriptions	
b	10 to 20 prescriptions	
c	21 to 50 prescriptions	
d	More than 50 prescriptions	

Data: Single punch.

090177e199ebc283\Approved\Approved On: 11-Apr-2022 22:32 (GMT)

[QUESTION APPLIES TO ALL COUNTRIES]

Q3. Within the last 12 months, how many **patients** have you treated with tofacitinib for ulcerative colitis? Please select one.

a	Fewer than 5 patients	
b	5 to 10 patients	
c	11 to 20 patients	
d	More than 20 patients	

Data: Single punch.

[QUESTION APPLIES TO ALL COUNTRIES]

Q4. Which of the following statements best describes your involvement in tofacitinib treatment for most of your patients? Please select one.

a	I'm involved only in the initiation of tofacitinib treatment. I refer patients to another practice for follow up and monitoring.	
b	I'm involved in both the initiation and maintenance of tofacitinib treatment.	
c	I'm involved only in the maintenance and monitoring of patients who were prescribed tofacitinib by another HCP.	

Data: Single punch.

[QUESTION APPLIES TO ALL COUNTRIES]

Q5. Have you ever participated in a Pfizer-sponsored tofacitinib clinical trial as a healthcare provider? Please select one response.

a	Yes	
b	No	
c	I'm not sure	

Data: Single punch.

[QUESTIONS ABOUT KNOWLEDGE OF KEY RISK MESSAGES FOR TOFACITINIB]

[QUESTION APPLIES TO ALL COUNTRIES]

Next, the third section of questions are designed to assess your understanding of the contraindications and risks of tofacitinib.

Q6. Please select the best response (True, False, I don't know) for each of the following statements about contraindications of tofacitinib.

		True	False	I don't know
a	Tofacitinib may be administered to patients with severe hepatic impairment.			
b	Tofacitinib is contraindicated in patients who are pregnant or lactating.			
c	Tofacitinib is contraindicated in patients with moderate renal impairment.			
d	Tofacitinib is contraindicated in patients with active tuberculosis (TB) or other severe infections such as sepsis or opportunistic infections.			

Data: Single punch per row.

Data: Answer options will be displayed in a random order for each survey participant.

Answer: Points a and c are wrong answers.

[QUESTIONS ABOUT KNOWLEDGE OF KEY RISK MESSAGES FOR TOFACITINIB]

[QUESTION APPLIES TO ALL COUNTRIES]

Q7. Please select the best response (True, False, I don't know) for each of the following statements about risks and use of tofacitinib.

		True	False	I don't know
a	Tofacitinib can be used in combination with biologic drugs or potent immunosuppressants, such as azathioprine, cyclosporine, 6-mercaptopurine, or tacrolimus.			
b	The possibility exists for tofacitinib to affect host defenses against malignancies.			
c	Live vaccines should not be given concurrently with tofacitinib.			
d	Prior to administering tofacitinib, it is NOT necessary to check patients' laboratory parameters including lymphocytes, neutrophils, and haemoglobin.			
e	Tofacitinib should be used with caution in patients who may be at increased risk for gastrointestinal perforation.			
f	When taking tofacitinib, the risk of herpes zoster is increased when the lymphocyte count (ALC) is lower than 1.0 cells x 10 ⁹ /L.			
g	Tofacitinib should only be considered in patients who are 65 years of age or older if there is no suitable alternative.			
h	Assuming there are other treatment options, tofacitinib 10 mg twice daily can be used in patients with venous thromboembolism (VTE) risk factors.			

Data: Single punch per row.

Data: Answer options will be displayed in a random order for each survey participant.

Answer: Points a, d, and h are wrong answers.

[QUESTIONS ABOUT ADHERENCE TO KEY RISK MESSAGES FOR TOFACITINIB]

[QUESTION APPLIES TO ALL COUNTRIES]

For the fourth set of questions, please think about your own clinical practice.

Q8. In your clinical practice, **before starting** a patient on tofacitinib, which of the following do you check or ask?

		Yes	No
a	Does this patient have gastroesophageal reflux disease (GORD)?		
b	Is the patient at an increased risk for skin cancer?		
c	Are this patient's immunisations up to date?		
d	Does this patient have a history of hyperthyroidism?		
e	Is this patient at an increased risk for venous thromboembolism (VTE)?		
f	If the patient is over 65 years of age, are there suitable alternative treatments to tofacitinib?		

Data: Single punch per row. Data: Answer options will be displayed in a random order for each survey participant.

Desired responses: b, c, e, f.

[QUESTIONS ABOUT ADHERENCE TO KEY RISK MESSAGES FOR TOFACITINIB]

[QUESTION APPLIES TO ALL COUNTRIES]

Q9. In your clinical practice, do you perform the following tests to make a decision about whether to **initiate** a patient on tofacitinib (Yes/No)?

		Yes	No
a	Screen for viral hepatitis		
b	Perform a urinalysis		
c	Screen for latent or active tuberculosis (TB)		
d	Check lymphocyte count		
e	Check absolute neutrophil count		
f	Check haemoglobin level		
g	Check blood glucose level		

Data: Single punch per row.

Data: Answer options will be displayed in a random order for each survey participant.

Desired responses: a, c, d, e, f.

[QUESTIONS ABOUT KNOWLEDGE OF KEY RISK MESSAGES FOR TOFACITINIB]

[QUESTION APPLIES TO ALL COUNTRIES]

Q10. In your clinical practice, which actions would you take when faced with the following scenarios during tofacitinib **treatment maintenance**? **Assume in all scenarios that the patient is receiving tofacitinib 5 mg twice daily unless otherwise noted.**

Select the best response for each scenario: “I would discontinue tofacitinib,” “I would interrupt dosing,” “I would lower the dose,” OR “I would take no action.”

		I would discontinue tofacitinib	I would interrupt dosing	I would lower the dose	I would take no action
a	The patient’s neutrophil count is less than 0.50 cells x 10 ⁹ /L. This is confirmed by repeat testing.	•			
b	The patient’s lymphocyte count is between 0.50-0.75 cells x 10 ⁹ /L. This is confirmed by repeat testing.		•		
c	The patient’s lymphocyte count is between 0.50-0.75 cells x 10 ⁹ /L. This is confirmed by repeat testing. The patient is receiving tofacitinib 10 mg twice daily for ulcerative colitis.			•	
d	The patient develops a serious		•		

090177e199ebc283\Approved\Approved On: 11-Apr-2022 22:32 (GMT)

		I would discontinue tofacitinib	I would interrupt dosing	I would lower the dose	I would take no action
	infection, an opportunistic infection or sepsis.				
e	The patient develops severe renal impairment (creatinine clearance <30 mL/min) and is taking tofacitinib 10 mg twice daily for ulcerative colitis.				
f	The patient develops severe hepatic impairment (Child Pugh C).				
g	The patient's haemoglobin level is <8 g/dl. This is confirmed by repeat testing.				
h	The patient has a suspected venous thromboembolism (VTE).				

Data: Multiple punch.

Data: Answer options will be displayed in a random order for each survey participant.

Answer: The black circles indicate a desired response.

[QUESTIONS ABOUT ADHERENCE TO KEY RISK MESSAGES FOR TOFACITINIB]

[QUESTION APPLIES TO ALL COUNTRIES]

Q11. In your clinical practice, how frequently do you perform each of these activities when **initiating treatment** with tofacitinib? Please select the best response: “Always,” “Sometimes,” or “Never”.

		Always	Sometimes	Never
a	Give the tofacitinib patient alert card to the patient.	•	•	○
b	Advise the patient to inform you immediately if they experience any of the symptoms on the tofacitinib patient alert card.	•	•	○
c	Advise patients to carry the tofacitinib patient alert card with them, particularly when they visit a doctor, a hospital, or Accident and Emergency.	•	•	○
d	Discuss the signs and symptoms of venous thromboembolism (VTE) with the patient.	•	•	○

Data: Multiple punch.

Answer: The black circles indicate a desired response.

[SOURCE OF HCPs' INFORMATION ON THE SAFETY OF TOFACITINIB]

[QUESTION APPLIES TO ALL COUNTRIES, EXCEPT FOR GERMANY]

The final set of questions asks about sources of information on tofacitinib.

Q12. Which of the following is your **primary source** of safety and prescribing information for tofacitinib? Please select one.

a	Educational materials (documents designed for the patient and the physician, such as the tofacitinib prescriber brochure, the prescriber initiation and maintenance checklists, and the patient alert card)	
b	Summary of Product Characteristics (Label)	
c	National Health Authority website/National formulary website	
d	Pharmaceutical company website	
e	Do not know/recall the source	
f	Other	

Data: Single punch.

Data: Answer options will be displayed in a random order for each survey participant, with an exception for "Do not know" and "Other" – always keep these as the last two options.

[QUESTIONS ABOUT AWARENESS (RECEIPT) AND UTILISATION OF TOFACITINIB aRMM MATERIALS]

[QUESTION APPLIES TO ALL COUNTRIES]

Q13.1a. Have you ever received a **prescriber brochure for tofacitinib**? Please select one.

- Yes
- No
- I don't remember

Data: Single punch.

[QUESTION APPLIES TO ALL COUNTRIES EXCEPT POLAND]

Q13.1b. The **prescriber brochure for tofacitinib** was updated in 2020. Did you receive a prescriber brochure after February 2020? Please select one.

- Yes
- No
- I don't remember

Data: Single punch.
Ask only if Yes in Q13.1a.

[QUESTION APPLIES TO POLAND ONLY]

Q13.1b. The **prescriber brochure for tofacitinib** was updated in 2020. Did you receive a prescriber brochure after January 2020? Please select one.

- Yes
- No
- I don't remember

Data: Single punch.
Ask only if Yes in Q13.1a.

[QUESTION APPLIES TO ALL COUNTRIES]

Q13.2. Have you read **the prescriber brochure for tofacitinib**? Please select one.

- Yes, all of it
- Yes, some of it
- No, I did not read it
- I don't remember

Data: Single punch.

Ask only if Yes in Q13.1a.

[QUESTION APPLIES TO ALL COUNTRIES]

Q13.3. How useful or not useful do you find the **prescriber brochure for tofacitinib** in your clinical practice?

- Very useful
- Somewhat useful
- Not useful

Data: Single punch.

Ask only if Yes in Q13.1a.

[QUESTION APPLIES TO ALL COUNTRIES EXCEPT GERMANY]

Q14.1a. Have you ever received the **prescriber treatment initiation checklist for tofacitinib**? Please select one.

- Yes
- No
- I don't remember

Data: Single punch.

[QUESTION APPLIES TO ALL COUNTRIES EXCEPT GERMANY AND POLAND]

Q14.1b. Did you receive the **prescriber treatment initiation checklist for tofacitinib** after February 2020? Please select one.

- Yes
- No
- I don't remember

*Data: Single punch.
Ask only if Yes in Q14.1a.*

[QUESTION APPLIES TO POLAND ONLY]

Q14.1b. Did you receive the **prescriber treatment initiation checklist for tofacitinib** after January 2020? Please select one.

- Yes
- No
- I don't remember

*Data: Single punch.
Ask only if Yes in Q14.1a.*

[QUESTION APPLIES TO ALL COUNTRIES EXCEPT GERMANY]

Q14.2. How often do you use the **prescriber treatment initiation checklist for tofacitinib** when writing a new prescription of tofacitinib for a patient? Please select one.

- All of the time
- Most of the time
- Some of the time
- Never

*Data: Single punch.
Ask only if Yes in Q14.1a.*

[QUESTION APPLIES TO ALL COUNTRIES EXCEPT GERMANY]

Q14.3. How useful or not useful do you find the **prescriber treatment initiation checklist for tofacitinib** in your clinical practice? Please select one.

- Very useful
- Somewhat useful
- Not useful

Data: Single punch.
Ask only if Yes in Q14.1a.

[QUESTION APPLIES TO ALL COUNTRIES EXCEPT GERMANY]

Q15.1a. Have you ever received the **prescriber treatment maintenance checklist for tofacitinib**? Please select one.

- Yes
- No
- I don't remember

Data: Single punch.

[QUESTION APPLIES TO ALL COUNTRIES EXCEPT GERMANY AND POLAND]

Q15.1b. Did you receive the **prescriber treatment maintenance checklist for tofacitinib** after February 2020? Please select one.

- Yes
- No
- I don't remember

Data: Single punch.
Ask only if Yes in Q15.1a.

[QUESTION APPLIES TO POLAND ONLY]

Q15.1b. Did you receive the **prescriber treatment maintenance checklist for tofacitinib** after January 2020? Please select one.

- Yes
- No
- I don't remember

*Data: Single punch.
Ask only if Yes in Q15.1a.*

[QUESTION APPLIES TO ALL COUNTRIES EXCEPT GERMANY]

Q15.2. How often do you use the **prescriber treatment maintenance checklist for tofacitinib** when writing a maintenance prescription of tofacitinib for a patient? Please select one.

- All of the time
- Most of the time
- Some of the time
- Never

*Data: Single punch.
Ask only if Yes in Q15.1a.*

[QUESTION APPLIES TO ALL COUNTRIES EXCEPT GERMANY]

Q15.3. How useful or not useful do you find the **prescriber treatment maintenance checklist for tofacitinib** in your clinical practice? Please select one.

- Very useful
- Somewhat useful
- Not useful

*Data: Single punch.
Ask only if Yes in Q15.1a.*

[QUESTION APPLIES TO GERMANY ONLY]

Q14.1.i.a. Have you ever received the **prescriber treatment checklist for tofacitinib**? Please select one.

- Yes
- No
- I don't remember

Data: Single punch.

[QUESTION APPLIES TO GERMANY ONLY]

Q14.1.i.b. Did you receive the **prescriber treatment checklist for tofacitinib** after February 2020? Please select one.

- Yes
- No
- I don't remember

Data: Single punch.
Ask only if Yes in Q14.1.i.a.

QUESTION APPLIES TO GERMANY ONLY]

Q14.2.i. How often do you use the **prescriber treatment checklist for tofacitinib** when writing a new prescription of tofacitinib for a patient? Please select one.

- All of the time
- Most of the time
- Some of the time
- Never

Data: Single punch.
Ask only if Yes in Q14.1.i.a.

QUESTION APPLIES TO GERMANY ONLY

Q14.3.i. How often do you use the **prescriber treatment checklist for tofacitinib** when writing a maintenance prescription of tofacitinib for a patient? Please select one.

- All of the time
- Most of the time
- Some of the time
- Never

*Data: Single punch.
Ask only if Yes in Q14.1.i.a.*

QUESTION APPLIES TO GERMANY ONLY

Q14.4.i. How useful or not useful do you find the **prescriber treatment checklist for tofacitinib** in your clinical practice? Please select one.

- Very useful
- Somewhat useful
- Not useful

*Data: Single punch.
Ask only if Yes in Q14.1.i.a.*

[QUESTION APPLIES TO ALL COUNTRIES]

Q16.1a. Have you ever received a supply of **tofacitinib patient alert cards**? This is a card which is designed to be given to patients. Please select one.

- Yes
- No
- I don't remember

*Data: Single punch.
Deliberately skipping a question number in Germany.*

[QUESTION APPLIES TO ALL COUNTRIES EXCEPT POLAND]

Q16.1b. Did you receive a supply of **tofacitinib patient alert cards** after February 2020?
Please select one.

- Yes
- No
- I don't remember

Data: Single punch.
Ask only if Yes in Q16.1a.

[QUESTION APPLIES TO POLAND ONLY]

Q16.1b. Did you receive a supply of **tofacitinib patient alert cards** after January 2020?
Please select one.

- Yes
- No
- I don't remember

Data: Single punch.
Ask only if Yes in Q16.1a.

[QUESTION APPLIES TO ALL COUNTRIES]

Q16.2. How useful or not useful did you find the **tofacitinib patient alert card** in your
clinical practice?

- Very useful
- Somewhat useful
- Not useful

Data: Single punch.
Ask only if Yes in Q16.1a.

[QUESTION APPLIES TO ALL COUNTRIES]

Q17.1 Are you aware of a **prescriber website for tofacitinib** where you can obtain prescribing information and where you can view and/or download the tofacitinib prescriber brochure, prescriber treatment checklists, and patient alert card? Please select one.

- Yes
- No

Data: Single punch.

[QUESTION APPLIES TO ALL COUNTRIES]

Q17.2. Have you ever visited the **prescriber website for tofacitinib**? Please select one.

- Yes
- No
- I don't remember

Data: Single punch.
Ask only if Yes in Q17.1.

[QUESTION APPLIES TO ALL COUNTRIES]

Q17.3. How useful or not useful do you find the **prescriber website for tofacitinib** in your clinical practice? Please select one.

- Very useful
- Somewhat useful
- Not useful

Data: Single punch.
Ask only if Yes in Q17.2.

Thank you for your participation in this survey

IQVIA Team

Appendix 3. Key Risk Messages and Other Questions About Awareness (Receipt), Utilisation, Practice Characteristics-Crosswalk of Survey Questions to Study Outcomes (Rheumatoid Arthritis and/or Psoriatic Arthritis)

The listed key risk messages were extracted from the Xeljanz Prescriber Brochure. Messages in bold have a corresponding survey question(s). All questions that correspond to key risk messages 1-9 apply to all countries as they are written (i.e., the questions are not worded differently per country). Remaining questions apply to all countries, unless otherwise noted.

